#### Secondary outcomes:

**Specific aim 2:** Determine if this protocol for ketamine holds its effectiveness over time post infusion.

**Hypothesis 2:** The effects of ketamine can last up to a week post infusion.

Primary outcome measures of SI will be through self-administered Beck Scale for Suicidal Ideation (BSS or BSSI or SSI). The self-administered version of Montgomery- Åsberg Depression Rating Scale (MADRS) will be used to measures degree of concomitant depression symptoms. These patient-level data will serve as baseline comparatives. Subjects shall be randomized by the pharmacy and designated to either ketamine treated or saline placebo arm, with both the treating nurse and physician blinded. The experimental arm shall receive 0.5 mg/kg IV ketamine infusion over 40 minutes. To test for effectiveness within groups, we will measure outcomes at two different time points, 4 and 24 hours post infusion. To evaluate effectiveness between groups we will compare results between treatment and placebo arms. To test for specific aim 2, and to maximize response rate, a phone call will be made, one week after the initial questionnaire was done.

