## Experimental Procedure

1. Baseline evaluation of suicidal severity (BSSI) & degree of depressive symptoms (MADRS-S) will be evaluated through self-administered questionnaires.
2. The experimental and placebo arms will receive a single dose of IV ketamine, 0.5 mg/kg in 100 cc NS or 100 cc of NS infused over 40 minutes.
3. Post ketamine re-evaluation of outcome measures at four and twenty-four hours will determine clinical effectiveness of ketamine intervention
4. Inspection of admission and transfer time provides time measurement for LOS. This secondary measure is needed to determine efficiency of intervention.
5. Post ketamine re-evaluation of outcome measure at one-week post infusion will elucidate ketamine's durability of effect.

**Table 2:** Description of activities at time points during the study

|  | Study Visit 1
Baseline ( $t_0$ ) | Study Visit 1
4 hours ( $t_1$ ) | Study Visit 1
24 hours ( $t_2$ ) | Study Visit 2
1 week ( $t_3$ ) |
|--|-------------------------------------|------------------------------------|-------------------------------------|-----------------------------------|
|  |                                     |                                    |                                     |                                   |

|  |   |   |   |   |
|--|---|---|---|---|
| Eligibility review and confirmation                    | X |   |   |   |
| Education regarding research & Informed Consent signed | X |   |   |   |
| History & Physical                                     | X |   |   |   |
| Randomization  | X |   |   |   |
| Dispense study drug                                    | X |   |   |   |
| IV Ketamine  | X |   |   |   |
| Vital Signs & ADR* monitored                           | X | X | X |   |
| Review adverse events                                  | X | X | X |   |
| Psychometric testing                                   | X | X | X | X |

\*ADR: Adverse drug reaction

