**11.5 Please provide a justification for your sample size**

Number of Subjects and Justification

This trial aims to have a minimum of 62 individuals. N calculation was done using R's built in statistical power pack. (Appendix D: N Calculation) Significance level and power used were the standard 0.05 and 0.8 respectively. Prior studies showed very large effect sizes. Their Cohen's d within groups and between groups were 1.23 and 1.45 respectively. The power of a study depends on effect size as well as sample size. Because their effect size is sufficiently large, they are able to detect differences from even a small sample.

When using this effect size, N calculations resulted in 8.5 to 11.4 individuals, which correlates to 17 to 22.8 individuals. However, the design of our study varies from past studies, in that we include a broader patient population. Instead of simply at individuals diagnosed with a mood disorder.

Based on suggested Cohen's d values, in order to have a large effect size in the T-test and ANOVA tests, N should be 25.5. In order to determine large correlations, N needs to be at least 28.2. This correlates to 52 to 56 subjects. Applying an estimated 10% subject dropout rate, the estimated number of subjects needed for the study is 62. Full effect and sample size breakdown are shown in Table 4.

**Table 4:** Effect and Sample Size Breakdown

| Test              | Effect size                     | N    |
|-------------------|---------------------------------|------|
| Two sample T-Test | Large (d = 0.8)                 | 25.5 |
| Two sample T-Test | Medium (d = 0.5)                | 63.7 |
| Two sample T-Test | Average within groups (d=1.23)  | 11.4 |
| Two sample T-Test | Average between groups (d=1.45) | 8.5  |
| ANOVA             | Large (f = 0.4)                 | 25.5 |
| ANOVA             | Medium (f = 0.25)               | 63.7 |

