### 11.6 Data Analysis Plan: Complete description: Background, Objectives, Design, Step by Step how the project is going to be done, Data analysis plan:

**Table 6:** Test Plan of Data Analysis

| Question to be answered   | Type of Analysis                                   | Independent (x)  | Dependent (y)      | Relationship     |
|---|--|--|--------------------|------------------|
| Is there a difference effect of ketamine in those who are high suicide vs. high depressed?                  | McNemar test                                       | High Suicide   | High depressed     | Within           |
| Is there a difference in the placebo between the same two groups?   | McNemar test                                       | High Suicide group                                     | High Suicide group | Within           |
| Is there any difference between ketamine vs. placebo on BSSI & MADRS?                                       | One-way MANOVA                                     | Group  | BSSI; MADRS        | Between          |
| Is there a difference in SI between Ketamine vs placebo   | 2 Independent sample t test                        | Group  | BSSI @ T4          | Between          |
| Is there a difference in depression between Ketamine vs placebo   | 2 independent sample t test                        | Group  | MADRS @ T4         | Between          |
| Is there a difference in effect from placebo when accounting for covariates?                                | MANCOVA  | Fixed factor: Group
Covariates: Demographics        | BSSI, MADRS @ T4   | Between          |
| Is there a difference in effect from ketamine @ the different time points?                                  | Mixed model
Or
Repeated measure ANOVA | Fixed factor: Group                                    | BSSI               | Within & between |
| Is there a difference in group at the different time points, when MADRS is a covariate?                     | Mixed model                                 | Fixed factor: Group
Covariates: MADRS               | BSSI               | Within & between |
| Is there a difference in group at the different time points, when MADRS, and demographics are considered? * | Mixed model                                 | Fixed factor: Group
Covariates: MADRS, demographics | BSSI               | Within & between |

\*This case requires a larger sample size.

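### Table 6's repeated-measures rows write no time term, group-by-time term, baseline covariate or one-week contrast, so the test of Hypothesis 2 is left unspecified

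*Combined protocol and SAP*

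**What the plan says.** Section 9.3 places Hypothesis 1 at 24 hours. It states Hypothesis 2 as "The effects of ketamine can last up to a week post infusion". Section 10.1 (Experimental Procedure, item 5) relies on the last assessment for durability: "Post ketamine re-evaluation of outcome measure at one-week post infusion will elucidate". Both arms complete BSSI at baseline, 4 h, 24-36 h and one week.

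Table 6 in section 11.6 has three repeated-measures rows with BSSI as the dependent variable:

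- The first asks "Is there a difference in effect from ketamine @ the different time points" and offers a mixed model or a repeated-measures ANOVA.
- The second asks "Is there a difference in group at the different time points, when MADRS is a covariate" and offers a mixed model only.
- The third adds demographics to MADRS, offers a mixed model only, and is footnoted as needing a larger sample.

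In all three the independent-variable column reads "Fixed factor: Group", plus the listed covariates in the second and third. All three are labelled as both within- and between-subject comparisons. Sections 11.1, 11.5 and 11.6 name no time term, group-by-time term, baseline BSSI covariate or one-week arm comparison. Section 11.5 says the linear model for repeated measures is used only if enrolment reaches 74, and describes it as handling uneven spacing and random effects. The planned total is 62.

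**The concern.** The row questions concern particular time points, but the terms written down do not produce an answer at any particular time point. Fitted literally, a model of BSSI on group estimates one arm difference averaged over whichever visits are entered. That average can be significant wholly because of 4 h and 24 h, and then be reported as a lasting effect when the arms no longer differ at one week. It can also miss an effect that is present only at one week.

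Adding time by using the repeated-measures ANOVA does not settle the matter. Its interaction test asks whether the arm difference changes over time, which is a different question from whether a difference remains at one week. The analyst would therefore choose the quantity that answers Hypothesis 2 after the data are in.

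**Working it through.** **The plan's own figure.** Section 11.5 states "Significance level and power used were the standard 0.05 and 0.8 respectively". Two-sided, d = 0.8 gives 25.52 per arm (printed 25.5), and a two-group ANOVA with f = 0.4 gives the same. For "In order to determine large correlations, N needs to be at least 28.2", r = 0.5 (assumed) gives 28.25. Then 2 × 28 = 56 and 56 × 1.1 = 61.6, which rounds up to 62. The stated size reproduces. These are between-group calculations with no time or interaction term, so no corrected N follows from this point.

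**Inputs for the illustration.**

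- 28 per arm: "Applying an estimated 10% subject dropout rate, the estimated number of subjects needed for the study is 62", and 62 × 0.9 = 55.8, about 56.
- d = 0.8: the plan's large effect, here assumed at 4 h and 24 h.
- Zero effect at baseline and at one week: assumed.
- Equal correlation r between visits, 0.3 to 0.7, SD 1: assumed.

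**Group-only term.** With k visits it estimates the mean of the visit effects. The variance of a subject's mean is (1 + (k − 1)r)/k. The standardised effect is the mean effect divided by the square root of that variance. The noncentrality is the standardised effect × √(28/2), on 54 degrees of freedom.

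- Baseline among the outcomes (k = 4): mean effect (0 + 0.8 + 0.8 + 0)/4 = 0.40.
- Post-baseline only (k = 3): mean effect (0.8 + 0.8 + 0)/3 = 0.533.

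| k | r | variance | standardised effect | group term significant |
|---|---|---|---|---|
| 4 | 0.3 | 0.475 | 0.580 | 57% |
| 4 | 0.5 | 0.625 | 0.506 | 46% |
| 4 | 0.7 | 0.775 | 0.454 | 39% |
| 3 | 0.3 | 0.533 | 0.730 | 77% |
| 3 | 0.5 | 0.667 | 0.653 | 67% |
| 3 | 0.7 | 0.800 | 0.596 | 59% |

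Simulation (20,000 trials per setting) agrees to within rounding. The one-week arm contrast rejected in 4.6% to 5.1% of the same trials, its nominal error rate.

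**The opposite case.** With d = 0.8 at one week only and baseline among the outcomes, the group term is significant in 19%, 15% and 13% of trials (r = 0.3, 0.5, 0.7). The one-week contrast detects the effect in 83-84%.

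**Omnibus group-by-time test (simulated; r = 0.3, 0.5, 0.7).**

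| Visits in the model | Effect gone at one week | Constant 0.8 at all post-baseline visits |
|---|---|---|
| Baseline as a level | 86%, 96%, 99.8% | 73%, 87%, 98% |
| Post-baseline only | 73%, 87%, 98% | about 5% |

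With baseline as a level, the test is usually significant whether or not the effect lasts. With post-baseline visits only, it is significant when the effect has gone and rejects only at the error rate when the effect is fully sustained. On neither layout does it test Hypothesis 2.

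**The case against.** The strongest reply is that time is there in substance. All three questions refer to time points. The within-and-between label means little without a within-subject factor. The same fixed-factor wording appears in the purely between-subject MANCOVA row, so it may name only the between-subject factor. At 62 subjects the 74-subject condition makes repeated-measures ANOVA the likely method for the first row, and that method contains a time factor by construction. All of this stands. A reader might infer that the rows cannot show an effect at different time points. The documents do not support that, because they leave time unwritten without excluding it. The reply does not supply a test of Hypothesis 2, however, because the ANOVA's omnibus terms do not isolate one week.

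A reader might also infer that Hypothesis 1 loses power. If baseline is an outcome level and d is 0.8, 0.8 and 0.4 at the three later visits (r = 0.5), the group term has about 64% power against 84% for a t test at 24 h. That depends on treating baseline as an outcome, which the plan does not say. With post-baseline visits only, the figure is 85% against 84%. Table 6 also has a separate t test of BSSI between arms. No power loss for Hypothesis 1 is claimed.

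Finally, a reader might infer that Hypothesis 2 certainly has no row. The t-test row is set at T4, which is undefined: Table 2 runs from t0 to t3. If T4 is the fourth assessment, that row compares the arms at one week, but the 24 h comparison then has no named row. If T4 is 4 hours, neither 24 h nor one week has one. On neither reading are both hypotheses covered by name.

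**Conclusion.** The point holds as under-specification. Table 6 writes no time term, interaction, baseline BSSI covariate or one-week contrast in its repeated-measures rows. The two results an analyst would most naturally report, the group term and the omnibus interaction, do not answer Hypothesis 2. If the effect has gone by one week, a group-only term is still significant in about 39-57% of trials with baseline included, or 59-77% without it, against about 5% for a one-week contrast.

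Those percentages illustrate the problem and do not predict this trial's results. They rest on 28 per arm, d = 0.8 at the two early visits, zero at one week, equal correlations of 0.3 to 0.7, and a literal group-only fit. The conclusion that visit-specific contrasts are needed does not depend on the exact values.

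**What to change.** Designate one primary repeated-measures model of post-baseline BSSI:

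- Terms: group, visit as a categorical factor (4 h, 24 h, one week), group-by-visit, baseline BSSI as a covariate, and the mood-disorder stratum, which section 11.1 already promises to adjust for. Name subject as the repeated unit and state the covariance structure.
- Read Hypothesis 1 from the 24 h arm contrast and Hypothesis 2 from the one-week arm contrast, each with a 95% CI. State that neither the group main effect nor the omnibus interaction is used for either claim.
- Remove the 74-subject condition in section 11.5 for this model, so that it runs at 62. The condition matches the Table 5 row with u = 4 and v = 34, where the plan's own formula gives 34 + 4 + 1 = 39 and 2 × 39 = 78, not the printed 37 and 74.
- Define T4 in the t-test and MANCOVA rows.
- Label the MADRS-adjusted and demographics-adjusted rows as supportive.

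The cost is a small amount of added specification in Table 6 and section 11.5. The data are already collected, and no patients or visits are added.

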## 12.0

### Participant Information

#### 12.1 Subject Population:

Participants will be adults, whom are 18 years or older, military personnel or civilians eligible for care in the military treatment facility.

#### 12.2 Age Range:

Check all the boxes that apply. If the age range of potential subjects (specimens, records) does not match the range(s) selected, please specify in the text box.

- 0-17
- 18-24
- 25-34
- 35-44
- 45-54
- 55-64
- 65-74
- 75+

#### 12.3 Gender:

- Male
- Female
- Other

#### 12.4 Special categories, check all that apply

- Minors /Children
- Students
- Employees - Civilian
- Employees - Contractor
- Resident/trainee
- Cadets /Midshipmen
- Active Duty Military Personnel
- Wounded Warriors
- Economically Disadvantaged Persons
- Educationally Disadvantaged Persons
- Physically Challenged (Physical challenges include visual and/or auditory impairment)
- Persons with Impaired Decisional Capacity
- Prisoners
- Pregnant Women, Fetuses, and Neonates
- Non-English Speakers
- International Research involving Foreign Nationals - Headquarters Review is necessary

You must also consider the requirements of DoDI 3216.02, paragraph 7.e.

You must also consider the requirements of DoDI 3216.02, Enclosure 3, paragraphs 7.e. and 12.

You must also consider the requirements of DoDI 3216.02, Enclosure 3, paragraph 7.e.

Depending on your intended subjects' status, you may also need to consider the requirements of DoDI 3216.02, Enclosure 3, paragraph 7.e.

You must also consider the requirements of 32 CFR 219.111(b).

You must also consider the requirements of 32 CFR 219.111(b).

## 12.5 Inclusion Criteria:

| Order Number                             | Criteria   |
|--|--|
| Subject Inclusion and Selection Criteria |  |
| 1  | 
1. Patient demographics will consist of Active, Reserve, or retired military personnel or their dependents.
 Subjects must meet the following inclusion criteria:
 
2. Adult (18 to 89 years old)
 3. Present with active SI
 4. Deemed to be admitted to inpatient psychiatric unit
 |

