The BSSI will measure the severity of SI. It is based on the interviewer rated version of the original Scale for Suicidal Ideation (SSI), which is one of the few document suicide assessment tools with predictive validity for suicide completion.42 The internal reliability, test and retest validity, as well as invariance over time has been demonstrated for the BSS. 43, 45 Furthermore, the first five items of the BSSI are a common clinical screening for the presence of suicidal thoughts.40 For these reasons, the BSSI was chosen as our primary outcomes measure. Two studies have indicated that the cut off between high and low risk is a BSS  $\geq 2$ .43, 45 A recent investigation has determined BSSI  $\geq 6$  is predictive of future suicide attempts. 53 These two values will serve in our analysis.

The Montgomery- Åsberg Depression Rating Scale (MADRS) is a widely known 10 item clinician administered measure of depression severity.46 Since its development in the late 1970s, it has become more popular than the gold standard, Hamilton rating scale for Depression (HAM-D). It is considered to be more sensitive to change, just as effective, and simpler to use clinically.47 However, the reliability depends on good interrater agreement.48 Difficulties in clinical trial to show signal detection for known effective drugs have implicated clinician administered measurement as a possible source of error. To avoid poor interrater reliability, rater bias, and variable interview quality,48 this trial will utilize the self-administered version of the MADRS-S.49 This has 9 items and

a total score ranging from 0 to 27.50 The scoring of MADRS-S has shown to be similar to that of physician scoring.

The emotional pain of the suicidal patient requires empathetic care that may not always be possible with the time pressures, volume, and pragmatic nature of the ED environment. A pharmacologic intervention with rapid effects to decrease SI would play a vital role in improving the standard of care for this vulnerable population.

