#### Primary outcome:

**Specific aim 1:** The objective of this investigation is to identify the clinical effectiveness of sub-dissociative dose IV Ketamine as an adjunctive treatment for the acutely suicidal patient in the ED.

**Hypothesis 1:** There will be a clinically significant decrease in suicidal ideation (SI) in those treated with Ketamine after 24 hours.

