Suicidal patients, subjectively identified by clinician, upon admission to the ED will be medically cleared by the EM physician, and then meet with the mental health liaison to be screened for admission to the psychiatric department, per normal standard of care. Study investigators will not be available around the clock, but when available will begin the pre-screening method for this investigation. The treating physician will pre-screen them for inclusion and exclusion criteria per an IRB approved check list (Appendix D: Criteria Checklist).

The patient will be approached for informed consent in accordance to with 21 CFR 50. They will be provided with a written document that embodies the elements of the informed consent. The consent will be presented orally to the subject with a witness. Once presented the subject will be given a reasonable time to review the contents and inquire information. Upon signing of the form, a copy shall be given to them.

Once consent is obtained, they will be presented with a paper form to complete the BSSI and MADRS-S. These measures will serve as baseline severity of suicidal wishes and plans, and degree of depression symptoms. Questionnaires will be stored in locked drawer's in the locked office the Division Officers in the Emergency Department, the Inpatient Mental Health ward, or the study coordinator.

Once the patient is deemed medically cleared by the treating physician, the study treatment will be ordered by an ED provider, per the randomization schedule, and administered by an ED nurse (Please see below for more detailed methodology). Those in the experimental arm will be treated with 0.5 mg/kg IV infusion of ketamine over 40 minutes. Those in the control arm will be treated with 100 cc Saline infusion over 40 minutes. (Table 1) Since there are no pharmaceutical treatment specific for acute suicide, it is in accordance to the Declaration of Helsinki (DOH) to utilize a saline placebo control. Vitals will be checked every 5 minutes during infusion. Questionnaires will be repeated at four time points for both arms, once in the ED before drug administration, one at 4 (+/-1) hours post-infusion, whether in the ED or the psychiatric unit, another 24-36 hours after the infusion in the inpatient psychiatric unit, and lastly one-week (+1 day) post treatment by phone call.

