## 13.0 Recruitment and Consent

### 13.1 Please describe the recruitment process, including how subjects will be identified and selected for the study.

#### Subject Recruiting Methods

The method for subject recruitment is demonstrated in Figure 1. Explicitly they are as follows:

1. Patient Identification/Pre-screening
  1. Clinician will subjectively identify patients who present to the ED that express SI
  2. Clinician or nurse reviews EMR for documented inclusion/exclusion criteria
  3. Clinician will medically clear patient
2. Screening: The mental health liaison interviews patient, and along with the on-call mental health provider, determines whether or not patient requires inpatient psychiatric hospitalization.

3. Screen positive: Eligible patients, who are being hospitalized on inpatient psychiatry, are approached for consent. If intoxicated on presentation, they are approached when clinically sober.
4. Consent is obtained:
  1. Patient will complete BSSI & MADRS-S
  2. Treatment is administered per protocol
  3. Vitals and ADR are monitored
5. Potential medication contraindications will be identified by treating physician, and a pharmacy consult will be obtained at the physician's discretion

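### No minimum baseline BSSI is set, so a patient scoring 0 or 1, below the plan's own high-risk cut-off, can be randomised with little or no room to show a decrease

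*Combined protocol and SAP*

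**What the plan says.** **Entry.** Section 12.5 requires that patients "Present with active SI" and, separately, "Deemed to be admitted to inpatient psychiatric unit". Section 13.1 describes the first step as "Clinician will subjectively identify patients who present to the ED that express SI", and the General Approach in 10.1 uses the same idea: "Suicidal patients, subjectively identified by clinician, upon admission to the ED will be medically cleared by the EM physician". Admission is a second judgement by other staff: "The mental health liaison interviews patient, and along with the on-call mental health provider, determines whether or not patient requires inpatient psychiatric hospitalization". No item in 12.5 or 12.6 names a scale or a score.

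**Outcome.** Section 9.3 makes the self-administered BSSI the primary outcome measure. Hypothesis 1 reads: "There will be a clinically significant decrease in suicidal ideation (SI) in those treated with Ketamine after 24 hours". The form is first completed after consent and serves as a baseline. Section 11.1 drops patients who do not complete a baseline but sets no level.

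**Cut-offs.** Section 9.2 states "Two studies have indicated that the cut off between high and low risk is a BSS" of 2 or more, cites 6 or more as predictive of attempts, and adds: "These two values will serve in our analysis". Section 11.1 attaches the value 2 to an average of four items instead.

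**The concern.** Eligibility is judged by clinicians; the primary outcome is what the patient writes on a form. The two can disagree. They can also be separated in time: under 13.1, patients intoxicated on arrival are approached only once sober. A patient who expressed suicidal ideation on arrival may score 0 or 1 on the form and still be randomised.

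A score of 0 cannot fall, and a score of 1 can fall by one point. If ketamine works, such a patient can show little or none of the benefit, and so pulls the between-arm difference towards zero. The sample has a small margin for this: 25.5 per arm are needed at d = 0.8, and about 28 are expected after dropout. In any analysis based on the values 2 or 6, a patient already below the value at baseline would also count as below it afterwards without having changed.

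**Working it through.** **Inputs from section 11.** Alpha 0.05 (two-sided assumed; it reproduces the plan's figures), target power 0.80, d = 0.8, 31 per arm, 10% dropout. Patients analysed per arm: 31 × 0.9 = 27.9, taken as 28.

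**Plan's own figure.** A two-sample t-test at d = 0.8 needs 25.52 per arm for 80% power, against 25.5 in Table 4. The stated total of 62 also fits: 56 / 0.9 = 62.2 and 56 × 1.1 = 61.6.

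**Room to fall.** With 2 or more as high risk, low risk means 0 or 1. The largest possible fall is 0 points from 0, 1 point from 1 and 2 points from 2. Under the other threshold, a patient below 6 can fall by up to 5 points.

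**Dilution.** Let f be the share of patients who contribute no treatment difference. The documents give no baseline BSSI distribution, so f is an assumption. With the SD unchanged, the effective size is d(f) = 0.8 × (1 − f). Power comes from the noncentral t with 2n − 2 = 54 degrees of freedom and noncentrality d(f) × √(n/2), n = 28.

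| f | d(f) | Power, 28 per arm | n per arm for 80% power |
|---|---|---|---|
| 0 | 0.80 | 0.836 | 25.5 |
| 5% | 0.76 | 0.798 | 28.2 |
| 10% | 0.72 | 0.754 | 31.3 |
| 20% | 0.64 | 0.652 | 39.3 |

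A share of about 5% uses up the planned margin, since 28.2 exceeds 28.

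**Sensitivity to the model.** A simulation that also lets floor patients widen the spread needs a second assumption: control mean 2 SD above the floor, floor patients fixed there in both arms. It gives unadjusted power of about 0.75, 0.68 and 0.53 at 5%, 10% and 20%. Adding adjustment for baseline to that floor model changes the picture:

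- Assumed baseline to follow-up correlation 0.5: about 0.92 at f = 0, 0.87 at 10%, 0.83 at 20%.
- Correlation 0.3: about 0.86, 0.78 and 0.71.

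The adjusted figures move by a hundredth or two with the details of the simulation. At f = 20% the loss is about 0.92 − 0.83 = 0.09 or 0.86 − 0.71 = 0.15, against 0.836 − 0.652 = 0.18 by simple dilution.

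**Does leaving these patients out cost power?** Under the same floor model and the unadjusted test, omitting floor patients without replacing them gives 0.79 against 0.67 when they are kept (f = 10%), and 0.73 against 0.53 (f = 20%).

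**The case against.** The strongest reply is that floor scores should be uncommon here. Patients express suicidal ideation, are interviewed by mental health staff and are judged to need admission; section 14.2 also excludes those admitted involuntarily. This stands. A reader might infer that entry rests on one clinician's impression alone, but the separate admission decision in 12.5 and 13.1 rules that out. Those requirements still set no BSSI level.

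Three other strong readings also fail:

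- A patient scoring exactly 2 is not low risk; section 9.2 makes 2 high risk.
- It is not true that the BSSI cannot record a fall in all low scorers. That is strict only at 0.
- These patients are not without information. The t-test in Table 6 compares follow-up scores, and a patient starting at 0 can worsen.

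The magnitude depends on the analysis. Table 6 includes a mixed model or repeated-measures ANOVA of BSSI over time, and adjusting for baseline recovers much of the loss. Against that, the t-test row is unadjusted and the MANCOVA row lists only demographics as covariates. The threshold concern is conditional too: Table 6 lists no between-arm comparison of proportions below 2 or 6, although section 9.2 says both values will be used.

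Finally, broad entry is deliberate. Section 11.5 explains the breadth, however, as not restricting to diagnosed mood disorder. That is a different matter from enrolling patients who report almost no suicidal ideation on the primary measure.

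**Conclusion.** The gap is real: a patient scoring 0 or 1 can be randomised, dosed and analysed, with at most one point of room for the decrease that Hypothesis 1 names. Its size is unknown. The power range of 0.80 to 0.65 rests on an assumed share of 5% to 20%, d = 0.8 among the other patients, 28 analysed per arm and an unadjusted t-test. At a share of zero nothing is lost.

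A reader might infer that the trial is underpowered for this reason. The documents do not support that, because they contain no evidence on the share and the admission requirement pushes it down. The point is a low-cost design improvement worth considering, not a necessary correction.

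**What to change.** Add to section 12.5: *baseline BSSI total of at least 2, completed and scored before randomisation*. This uses the plan's own boundary and a form every patient already completes. Patients below it would not be randomised and would continue with usual care. Two matters must be settled with it:

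- **Scoring.** State that the 2 is a total score. Section 9.2 reads that way, while section 11.1 ties it to an average of four items.
- **Order.** The General Approach in 10.1 puts the baseline form before the treatment order. Methods and Materials describes the order and pharmacy randomisation first, and section 10.14 assigns the identifier used on the questionnaires during randomisation. These need reconciling so that the score is known before allocation.

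For any analysis by the cut-off of 6, compare the arms on the proportion falling below 6 among patients at 6 or above at baseline.

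The costs are a few minutes of scoring, slightly slower accrual, some consented patients not randomised, and a result limited to patients who self-report suicidal ideation. A minimum of 2 also leaves some patients with only two points of room, so it reduces the floor problem without removing it. If the sponsor prefers to keep entry open, the least it should do is report the baseline BSSI distribution by arm and adjust the BSSI comparison for baseline.
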